8.2. Discontinuation from the Study

Patients will be discontinued from the study in the following circumstances:

- participation in the study needs to be stopped for medical, safety, regulatory, or other reasons consistent with applicable laws, regulations, and good clinical practice (GCP).
- the patient becomes pregnant during the study. See Section 9.2 regarding regulatory reporting requirements on fetal outcome and breast-feeding
- the investigator decides that the patient should be discontinued from the study
- the patient requests to be discontinued from the study
- the patient's legal representative requests that the patient be discontinued from the study

Patients who discontinue from the study early will have end-of-study procedures performed as shown in the Schedule of Activities (Section 2).

8.3. Lost to Follow-Up

A patient will be considered lost to follow-up if he or she repeatedly fails to return for scheduled visits and is unable to be contacted by the study site. Study site personnel are expected to make diligent attempts to contact patients who fail to return for a scheduled visit or who the site is otherwise unable to follow-up.

9. Study Assessments and Procedures

Section 2 provides the Schedule of Activities for this study.

Appendix 2 provides a list of the laboratory tests that will be performed for this study.

Appendix 4 provides the schedule for collection of samples in this study.

Unless otherwise stated in the following subsections, all samples collected for specified laboratory tests will be destroyed within 60 days of receipt of confirmed test results. Certain samples may be retained for a longer period, if necessary, to comply with applicable laws, regulations, or laboratory certification standards.

9.1. Efficacy Assessments

Tumor assessments will be performed for each patient at the times shown in the Schedule of Activities (Section 2). A secondary objective of the study is to document efficacy.

RECIST 1.1 (Eisenhauer et al. 2009) will be applied as the primary criteria for assessment of tumor response and disease progression. Local tumor imaging (investigator assessment with site radiological reading) will be used. Modified RECIST will be applied for patients with pleural mesothelioma whereby tumor thickness (perpendicular to chest wall or mediastinum) would be measured at 2 positions on 3 separate levels on transverse cuts of CT scan (Byrne 2004).

Computed tomography (CT) is the preferred imaging method for the majority of patients. Magnetic resonance imaging should only be used when CT is contraindicated or for imaging in the brain. The same imaging technique should be used for a patient throughout the trial. Imaging should include the chest, abdomen, and pelvis. Intravenous and oral contrast is required unless medically contraindicated.

At Study Baseline:

- Must be performed within 28 days prior to the first dose of study drug.
- Scans performed as part of routine clinical management are acceptable for use as initial tumor imaging if they are of diagnostic quality and performed within protocol-required time frame as described above.

During Study Treatment:

- Performed every 8 weeks (± 7 days), by the investigator, with confirmatory assessment obtained at the next routine scheduled imaging time point.
- Per RECIST v1.1, PR or CR should be confirmed by a repeat tumor imaging assessment, preferably at the next scheduled imaging visit, and not less than 4 weeks from the date the response was first documented. Thus, for Study JZDA, tumor imaging for confirmation of response may be performed at the earliest 4 weeks after the first indication of response, or at the next scheduled scan, whichever is clinically indicated.
- Continue to perform imaging until whichever of the following occurs **first**:
 - disease progression confirmed by the second radiographic examination

- the start of new anticancer treatment
- withdrawal of consent
- death
- study completion

If radiologic imaging verifies an initial assessment of PD, apply RECIST 1.1 with confirmatory scan for disease progression (Section 9.1.1).

During the Poststudy Treatment Period: Tumor assessments may continue for patients who are withdrawn from the study treatment for reasons other than disease progression every 6 to 12 weeks depending on standard of care.

See Section 10.3.2 for definitions of the efficacy endpoints.

9.1.1. RECIST 1.1 with Confirmatory Scan for Disease Progression

9.1.1.1. Rationale for RECIST 1.1 with Confirmatory Scan for Disease Progression

Response to immunotherapy may differ from responses typically observed with cytotoxic chemotherapy, including the following (Wolchok et al. 2009; Nishino et al. 2013):

- Response to immunotherapy may be delayed.
- Response to immunotherapy may occur after PD by conventional criteria.
- The appearance of new lesions may not represent PD with immunotherapy.
- Stable disease while on immunotherapy may be durable and represent clinical benefit.

Therefore, to adequately characterize additional patterns of response and progression specific to patients treated with immunotherapy, which cannot be captured by conventional criteria such as RECIST 1.1, alternative measures of tumor assessment have been developed: (i) RECIST 1.1 with confirmatory scan for disease progression and (ii) immune-related response criteria (irRC, Wolchok et al. 2009). For both measures (i) and (ii), clinically stable patients may continue treatment until disease progression (per standard RECIST 1.1) is confirmed. As the irRC are still being developed and validated for various tumor types, Study JZDA will use RECIST 1.1 with confirmatory scan for disease progression, which may discourage the early discontinuation of study treatment and provide a more complete evaluation of its efficacy than would be seen with conventional response criteria.

Table JZDA.9.1. Summary of Response Assessment by RECIST, RECIST with Confirmatory Scan for PD, and irRC

Definition	Used in Study JZDA		Not Used in Study JZDA
	RECIST v1.1	RECIST 1.1 with Confirmatory Scan for PD	irRC (Wolchock et al. 2009), irRECIST (Nishino et al. 2013) iRECIST (Seymour et al. 2017)
New lesion	The presence of new lesion defines progression	The presence of new lesion defines progression	The presence of new lesion does not define progression. The measurements of the new lesion(s) are included in the sum of the measurements.
Confirmation of PD	Not required	PD, in the absence of clinically significant deterioration, requires confirmation with repeat imaging after 4-6 weeks. After initial PD following RECIST v1.1, shift to “RECIST 1.1 with confirmatory scan for PD”.	Required

Abbreviations: irRC = immune-related response criteria; irRECIST = immune-related Response Evaluation Criteria in Solid Tumors PD = progressive disease; RECIST = Response Evaluation Criteria in Solid Tumors.

9.1.1.2. Application of RECIST 1.1 with Confirmatory Scan for Disease Progression

For Study JZDA, based on the unique response to immunotherapy and guidelines from regulatory agencies (for example, the EMA guideline on the evaluation of anticancer medicinal products in man for immune-modulating anticancer compounds [EMA 2013]), the following will be applied, in addition to standard RECIST 1.1 criteria:

- If radiologic imaging verifies initial PD, tumor assessment should be repeated 4 to 6 weeks later in order to confirm PD in the absence of clinically significant deterioration. Study treatment will continue between the initial assessment of progression and confirmation for progression (see Section 9.1.1.3).

“Clinically significant deterioration” is considered to be rapid tumor progression that necessitates treatment with anticancer therapy other than study treatment, or symptomatic progression that requires urgent medical intervention (for example, rapid disease progression or threat to vital organs or critical anatomical sites, such as central nervous system metastasis, respiratory failure due to tumor compression, or spinal cord compression).

- In the case of clinically significant deterioration, the patient will be discontinued from study treatment (Section 8.1).
- Patients who continue to receive clinical benefit and who do not have clinically significant deterioration despite evidence of objective PD by the confirmatory scan may continue study treatment at the discretion of the investigator, in consultation with the Lilly CRP/CRS.

In determining whether or not progression can be confirmed, the site study team should consider all target lesions, nontarget lesions, and new lesions.

9.1.1.3. Criteria Required to Receive Treatment during Confirmatory Scan Period

In order for patients to continue receiving LY3415244, the following criteria apply:

- absence of clinically significant deterioration (defined in Section [9.1.1.2](#))
- absence of clinical symptoms indicating clinically significant disease progression
- no decline in performance status
- no significant, unacceptable or irreversible toxicities related to study treatment
- patient must sign the addendum consent prior to being treated during this time period

9.2. Adverse Events

The investigator will use CTCAE, Version, 4.0 (NCI 2009) to assign AE terms and severity grades.

Investigators are responsible for:

- monitoring the safety of patients who have entered into this study and for alerting Lilly or its designee to any event that seems unusual, even if this event may be considered an unanticipated benefit to the patient.
- providing appropriate medical care to the patient during the study.
- documenting their review of each laboratory safety report.
- following, through an appropriate health care option, AEs that are serious or otherwise medically important, considered related to study treatment or the study, or that caused the patient to discontinue study drug before completing the study. The patient should be followed until the event resolves, stabilizes with appropriate diagnostic evaluation, or is reasonably explained. Frequency of follow-up evaluation is left to the discretion of the investigator.

Lack of drug effect is not an AE in clinical studies, because the purpose of the clinical study is to establish safety and toxicity.

After the ICF is signed, study site personnel will record via eCRF the occurrence and nature of each patient's preexisting conditions, including clinically significant signs and symptoms of the disease under treatment in the study. Study site personnel will record via eCRF any change in preexisting conditions and any new conditions as AEs. Investigators should record their assessment of the potential relatedness of each AE to study treatment or study procedure via eCRF.

The investigator will interpret and document whether or not an AE has a reasonable possibility of being related to study treatment or a study procedure, taking into account the disease,

concomitant treatment or pathologies. A “reasonable possibility” means that there is a cause and effect relationship between the study treatment and/or study procedure and the AE.

Adverse Event grading of toxicities related to estimated glomerular filtration rate (GFR) should be evaluated based on the Cockcroft-Gault method (Cockcroft and Gault 1976) or measured GFR.

Planned surgeries should not be reported as AEs unless the underlying medical condition has worsened during the course of the study.

Study site personnel must report any dose modifications or treatment discontinuation that results from AEs to Lilly or its designee via eCRF, clarifying, if possible, the circumstances leading to dose modification or discontinuation of treatment.

9.2.1. Serious Adverse Events

An SAE is any AE during this study that results in one of the following outcomes:

- death
- initial or prolonged inpatient hospitalization
- a life-threatening experience (that is, immediate risk of dying)
- persistent or significant disability/incapacity
- congenital anomaly/birth defect
- important medical events that may not be immediately life-threatening or result in death or require hospitalization, may be considered serious when, based upon appropriate medical judgment, they may jeopardize the patient and may require intervention to prevent one of the other outcomes listed in the definition above.

Although all AEs after signing the ICF are recorded in the eCRF, SAE reporting to Lilly begins after the patient has signed the ICF and has received study treatment. However, if an SAE occurs after signing the ICF, but prior to receiving study treatment, it needs to be reported ONLY if it is considered reasonably possibly related to study procedure.

Where permitted, study site personnel must notify Lilly or its designee of any SAE within 24 hours of investigator awareness of the event via a Lilly-approved method. If alerts are issued via telephone, they are to be immediately followed with official notification on study-specific SAE forms. This 24-hour notification requirement refers to the initial SAE information and all follow-up SAE information.

Pregnancy (during maternal or paternal exposure to study treatment) does not meet the definition of an AE but should be reported. To fulfill regulatory requirements any pregnancy should be reported following the SAE process to collect data on the outcome for both mother and fetus.

Investigators are not obligated to actively seek AEs or SAEs in patients once they have discontinued and/or completed the study (the patient summary eCRF has been completed). However, if the investigator learns of any SAE, including a death, at any time after a patient has

been discharged from the study, and he/she considers the event reasonably possibly related to the study treatment or study participation, the investigator must promptly notify Lilly.

Planned hospitalizations or procedures for preexisting conditions that were recorded in the patient's medical history at the time of study enrollment should not be considered SAEs. Hospitalization or prolongation of hospitalization without a precipitating clinical AE (for example, for the administration of study treatment or other protocol-required procedure) should not be considered SAEs.

Serious adverse events, including death, caused by disease progression should not be reported unless the investigator deems them to be possibly related to study treatment.

9.2.2. Suspected Unexpected Serious Adverse Reactions

Suspected unexpected serious adverse reactions (SUSARs) are serious events that are not listed in the IB and that the investigator identifies as related to study treatment or study procedure. The United States 21 CFR 312.32, the Regulation (European Union) No 536/2014 and the associated detailed guidance or national regulatory requirements in participating countries require the reporting of SUSARs. Lilly has procedures that will be followed for the recording and expedited reporting of SUSARs that are consistent with global regulatory regulations and the associated detailed guidance.

Regular communication will occur between investigators and the sponsor via various channels (that is, email, regularly scheduled teleconference, Safety Reporting Notification System, etc.) to ensure that all parties are aware of how patients are tolerating LY3415244. If in the event that sites need to be made aware of an emerging safety issue in a timely manner, Lilly will, upon confirmation of the event, communicate to site staff via email and/or direct telephone calls to ensure receipt of all of the information. Lilly will follow-up with individual sites until receipt of the information is confirmed and that the site has taken the appropriate safety measures.

9.2.3. Complaint Handling

Lilly collects complaints on study drugs and drug delivery systems used in clinical studies in order to ensure the safety of study participants, monitor quality, and facilitate process and product improvements.

Patients will be instructed to contact the investigator as soon as possible if he or she has a complaint or problem with the investigational product so that the situation can be assessed.

9.3. Treatment of Overdose

If a patient receives a higher dose of LY3415244 than that specified in the protocol, patients should receive appropriate supportive care measures for any AEs, as deemed necessary by the treating investigator.

9.4. Safety

9.4.1. Other Safety Measures

Refer to the Schedules of Activities (Section 2) regarding the timing of vital signs, laboratory tests, and other tests.

Perform ECGs as shown in [Appendix 4](#). Triplicate ECGs will be collected in Study JZDA. ECGs should be recorded according to the study-specific recommendations included in the ECG manual.

ECGs will be initially interpreted by a qualified physician at the site (the investigator or qualified designee) as soon after the time of ECG collection as possible (ideally while the patient is still present) to determine whether the patient meets entry criteria and for immediate patient management.

If a clinically significant quantitative or qualitative change from baseline is identified after enrollment, the investigator will assess the patient for symptoms (for example, palpitations, near-syncope, or syncope) and to determine if the patient can continue in the study. The investigator or qualified designee is responsible for determining if any change in patient management is needed and must document his/her review of the ECG printed at the time of evaluation.

Any clinically significant findings that result in a diagnosis and that occur after the patient receives the first dose of study treatment should be reported to Lilly or its designee as an AE via eCRF.

All digital ECGs will be electronically transmitted to a designated central ECG laboratory. The central ECG laboratory will perform a basic quality control check (for example, demographics and study details) and store the ECGs in a database. At a future time, the stored ECG data may be overread at the central ECG laboratory for further evaluation of machine-read measurements or to meet regulatory requirements.

The machine-read ECG intervals and heart rate may be used for data analysis and report writing purposes unless a central ECG laboratory cardiologist overread of the ECGs is conducted prior to completion of the final study report (in which case the overread data would be used).

For each set of replicates, the cardiologist will determine the R-R and QT intervals and heart rate on the ECGs. These data are not routinely reported back to the investigative site. However, any clinically significant finding that was not present on the fully overread ECG will be reported to the investigator and to Lilly. All data from the overreads will be placed in the Lilly database for analytical and study report purposes.

The investigator's (or qualified designee's) ECG interpretation will be used for decisions about study entry and immediate patient management will be based on the investigator's or qualified designee's ECG interpretation.

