Cardiac	Myocarditis, cardiac function abnormalities (for example, dysrhythmia, valvular abnormalities)	≥1		
 Discontinue study treatment and administer 
 IV methylprednisolone 2-4 mg/kg/day Consider immunosuppressives without immediate response to steroids (for example, mycophenolate, infliximab, or anti-thymocyte globulin) Consult with cardiology immediately and Lilly CRP/CRS; if available, transfer to cardiac care unit
Renal and urinary	Elevated creatinine, decreased urine output, blood in urine, edema, nephritis	1	<1.5 x baseline	Continue study treatment
		2-3	1.5 × ULN < × ≤ 6 × ULN or >1.5 × baseline	
 Withhold study treatment and administer prednisone 0.5-1 mg/kg/day Resume study treatment after the event resolves to Grade ≤1 If elevations persist for >7 days or worsen, follow the guidelines for a Grade 4 event
		4	>6 × ULN	Discontinue study treatment and administer prednisone 1-2 mg/kg/day

Dose Modification Guidelines and AE Management for Toxicities At Least Possibly Related to Study Drug

SOC	Toxicity	CTCAE Grade and/or Symptoms ^a		Treatment Plan ^b
		Grade	Symptoms	
Skin	Rash, pruritus		Moderate rash (diffuse, ≤30% BSA)	
 Withhold study treatment For rash on <10% of the patient's BSA, administer intermediate or high-potency topical corticosteroid For rash on 10%-30% of the patient's BSA, administer systemic corticosteroids Resume study treatment if the rash improves to mild (localized) and the corticosteroid dose is <7.5 mg/day
	Stevens–Johnson syndrome, toxic epidermal necrolysis, necrosis, bullous or hemorrhagic lesions			Discontinue study treatment and administer prednisone 1-2 mg/kg/day
Ophthalmological	Eye disorders (for example, uveitis, episcleritis)	≥2		
 If mild, consider topical steroids (for example, 1% prednisolone); otherwise, discontinue study treatment and administer 
 Oral or IV methylprednisolone 2-4 mg/kg/day Consult ophthalmologist and Lilly CRP/CRS.

Dose Modification Guidelines and AE Management for Toxicities At Least Possibly Related to Study Drug

Abbreviations: ADL = activities of daily living; ALT = alanine aminotransferase; AST = aspartate aminotransferase; BSA = body surface area; CRP = clinical research physician; CRS = Clinical Research Scientist;

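### Section 9.4.1's only rule for returning central ECG overread findings omits a clinically significant finding that is on the fully overread tracing (minor; wrong as written)

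*Protocol*

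**What the plan says.** All the relevant text is in Protocol Section 9.4.1. The site reads first: "ECGs will be initially interpreted by a qualified physician at the site", as soon as possible after recording. The investigator's or designee's "ECG interpretation will be used for decisions about study entry and immediate patient management".

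The central laboratory comes second. "All digital ECGs will be electronically transmitted to a designated central ECG laboratory", where they are quality-checked and stored. Later, "the stored ECG data may be overread at the central ECG laboratory", either to evaluate the machine measurements further or to meet regulatory requirements. No date is set. If a cardiologist's overread is done, the cardiologist determines R-R and QT intervals and heart rate for each replicate set, and the section says that these data do not routinely go back to the site. It then makes one exception: "any clinically significant finding that was not present on the fully overread ECG will be reported to the investigator and to Lilly".

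The use of the data is settled separately. Machine-read intervals and heart rate may be analysed unless an overread is completed before the final study report, "in which case the overread data would be used". "All data from the overreads will be placed in the Lilly database for analytical and study report purposes".

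**The concern.** A return rule for central readings exists to tell the investigator about something important that the cardiologist saw and the site may have missed. This one attaches to findings that were not on the fully overread tracing. Followed literally, it leaves out the findings it would most plausibly be meant to catch.

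What is at stake is the investigator's ability to act. Section 9.4.1 has the investigator assess the patient when a clinically significant change from baseline is identified. It also has significant findings that lead to a diagnosis after the first dose reported as adverse events. Section 9.2 has the investigator assess relatedness. Each step requires the investigator to know of the finding. In one narrow case treatment could change: the cardiac row of Table JZDA.7.4, which includes dysrhythmia, calls for discontinuation from Grade 1. That table applies only to potential immune-related events that are at least possibly related to study drug, and the overread would have to take place while the patient is still on treatment.

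**Working it through.** The plan gives no figure to reproduce and no arithmetic applies. The check has three steps.

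**Step 1. What can the fully overread ECG mean?** The protocol designates no tracing as such. On-study ECGs are recorded in triplicate, with all 3 replicates completed within 5 to 15 minutes (Appendix 4, footnote d). The possible readings are:

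- *Every replicate is fully read.* The duty then attaches only to findings that are on none of the fully read tracings. Whatever the cardiologist saw on them is outside the rule.
- *One replicate per set is fully read and the other 2 are looked at more briefly.* The duty then covers a finding seen only on those other 2. A finding on the fully read tracing is outside the rule, and so is one on all 3 replicates, although it is the most reproducible kind. The protocol does not describe this workflow.
- *The sentence was meant to say not present at baseline, or not noted by the site.* It mentions neither the baseline ECG nor the site's reading.

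Under the first two readings, a finding on the fully overread tracing has no stated duty of return. The third would close most of the gap, but the words do not say it.

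**Step 2. Does another provision supply the duty?**

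| Place | What it provides | Requires return of an individual overread finding? |
|---|---|---|
| Rest of Section 9.4.1 | Whether an overread is done, how its data are used, where they are stored | No |
| Section 2 schedules and Appendix 4 | Timing of ECG recording | No |
| Section 9.2.2 | General sponsor-to-site communication, including emerging safety issues | No |
| Section 9.4.2 | Periodic review of aggregate safety data | No |
| Section 10.3.1 | Summaries of ECG changes | No |
| SAP 5.12.7 | Listing and summary of abnormal ECGs from local testing | No |

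Outside Section 9.4.1, the current protocol text does not mention the overread. The SAP does not mention it at all.

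**Step 3. How far does the non-return default reach?** The statement that data are not routinely sent back directly follows the sentence on R-R, QT and heart rate, and most naturally refers to those measurements. It is therefore not a ban on returning diagnostic findings. The gap is a missing requirement, not a prohibition.

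**The case against.** The strongest case against concerns weight. The overread is not set up as a prospective safety reading: it may never happen, it has no date, and its stated purposes are measurement quality and regulatory need. The protocol deliberately keeps clinical decisions with the site physician, who reads the ECGs soon after recording and documents the review. For harm to follow, an overread must be done during treatment, it must show something significant that the site missed, and the sponsor, which holds the overread data, must then not pass it on. The ECG manual is not among the documents and may describe the central workflow. The intended meaning of the sentence cannot be established from the text.

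All of this stands, and it is why the point is minor. It does not repair the wording: none of these considerations creates a duty to return a finding that is on the fully overread tracing.

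A reader might draw stronger conclusions that the documents do not support:

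- *That significant overread findings will be withheld from sites.* The text does not bar feedback, and Section 9.2.2 keeps a general channel open.
- *That any Grade 1 rhythm abnormality on overread would require stopping treatment.* Table JZDA.7.4 is limited as described above, and Section 7.4 lets local guidelines supersede it where the investigator thinks this appropriate.
- *That overread measurements are lost to analysis.* Section 9.4.1 provides for their use and storage.

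**Conclusion.** The point holds as a minor error in operative text. The only ECG-specific return rule, taken literally, does not cover a clinically significant finding on the fully overread tracing, and the term on which the rule turns is undefined.

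No rate can be given. The documents do not say how many ECGs would be overread, when, or how often the central and site readings would differ. If no overread is done, nothing is affected. No endpoint, DLT rule, escalation decision or sample size depends on the sentence. The conclusion rests on the protocol and SAP text as provided; a clear rule in the ECG manual could reduce the practical consequence, though the protocol sentence would still need correcting.

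**What to change.** Replace the return sentence in Section 9.4.1 with wording such as: *If a central overread is done, any clinically significant finding on any replicate is to be reported to both the investigator and the sponsor.* The investigator can then compare the finding with the site's own reading and assess it under Section 9.2. This removes the undefined term, and the central laboratory does not need the site's interpretation.

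The change is one sentence, with any matching text in the ECG manual brought into line. It needs no extra ECGs. The downside is a small amount of duplicate reporting and reconciliation of findings already known to the site or present at baseline. It does not make the overread mandatory or timely, so a finding could still arrive after treatment has ended.

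Whether SAP 5.12.7, which is limited to local testing, should also list significant overread findings is a separate optional matter and is not needed for this fix.
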